Outcome: clinical examination)

Timepoint: Change from Day 1 at Day 180 +/- 24

Secondary Routine nerve conduction studies (NCS) –sural sensory amplitude

Outcome: (measured using Dantec Keypoint G4 Workstation)

Timepoint: Change from Day 1 at Day 180 +/- 24

Secondary Routine nerve conduction studies (NCS) – peroneal motor velocity

Outcome: (measured using Dantec Keypoint G4 Workstation)

Timepoint: Change from Day 1 at Day 180 +/- 24

Routine nerve conduction studies (NCS) - tibial motor minimum F-**Secondary** Outcome: wave latency (measured using Dantec Keypoint G4 Workstation)

Timepoint: Change from Day 1 at Day 180 +/- 24

Nerve excitability profile: Depolarising threshold electrotonus (TEd) **Secondary** Outcome: (peak), TEd (90-100 ms), hyperpolarising threshold electrotonus

> (Teh) (90-100 ms), TEd (10-20 ms), superexcitability, subexcitability, resting current-voltage (I/V) slope, strength duration time constant

(measured with QTRAC software using TROND protocol)

Timepoint: Change from Day 1 at Day 180 +/- 24

Secondary Quantitative sudomotor axonal reflex testing (QSART), measured at

Outcome: the foot in sweat volume in nL using the QSWEAT system.

Timepoint: Change from Day 1 at Day 180 +/- 24

Secondary Cutaneous silent period testing: upper and lower limb (measuring

Outcome: silent period onset latency and duration) Timepoint: Change from Day 1 at Day 180 +/- 24

5.2. Safety measures:

Safety Outcome: Adverse events (AEs) reported

Timepoint: Change from Day 1 at Days 30 +/- 14, 90 +/- 14, 180 +/- 24

Safety Outcome: Change in habitual visual acuity measured using a standard eye chart

Timepoint: Change from Day 1 at Days 30 +/- 14, 90 +/- 14, 180 +/- 24

Change in intraocular pressure (IOP) measured using a Goldmann **Safety Outcome:**

tonometer

Timepoint: Change from Day 1 at Day 180 +/- 24

Safety Outcome: Diabetic retinopathy graded using the Wisconsin Scale grading system

Change from Day 1 at Day 180 +/- 24

Secondary Blood samples (measuring fasting glucose, fasting lipid profile [LDL, **Outcome:**

HDL, total cholesterol, triglycerides], FBC, ESR, CRP, Vitamin B-12,

Folate, TSH, UEC, HbA1c, liver function, electrolytes)

Timepoint: Change from Day 1 at Day 180 +/- 24

5.3. Compliance measures:

Compliance Total omega-3 status obtained from blood finger spot test (Waite

Outcome: Lipid Analytical Services)

Change from Day 1 at Day 180 +/- 24 Timepoint:

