8.1. Statistical methods

A separate statistical analysis plan will be developed and finalised prior to study unmasking.

Data relating to participant demographics and baseline clinical characteristics will be analysed with a repeated measures model or ordered logistic regression model, as appropriate. For the primary outcome, analyses will be performed on data from right eyes. For slit lamp examination, analyses will be performed on the average of data from both eyes. For neurophysiological data, analyses will be performed on data from one limb only.

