11.2.1 Michigan Diabetic Neuropathy Score (MDNS) and routine nerve conduction studies (NCS)

[figure not shown]
The first part of the MDNS is a clinical examination, which is then followed by routine nerve conduction studies. Vibratory threshold perception is assessed with a 128 Hz tuning-fork. Light touch is assessed with a 10g monofilament applied to the dorsum of the great toe. Deep tendon reflexes and muscle strength testing formed the remainder of the clinical examination score. Nerve conduction studies are then performed using an electromyographic (EMG) device (Dantec Keypoint G4 Workstation), examining the right upper and lower extremities, and included median, peroneal and tibial motor studies, and sural, median and ulnar sensory studies. Abnormal parameters are defined as amplitudes, conduction velocities or latencies that exceeded two standard deviations from the normal values of our laboratory. Testing is performed with a target temperature of 32 degrees Celsius in the upper extremity and 30 degrees Celsius in the lower extremity. Participants are given a composite score (from class 0 to 3) based on their clinical examination and nerve conduction study results.

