11.2.2 Cutaneous Silent Periods (CSPs)

The CSP is recorded from both upper and both lower extremities using the same EMG device above. Filters are set at 20 Hz to 10 kHz, sweep speed is 300 ms, and sensitivity is 300 μ V. In the upper extremities, electrical stimulations are delivered to the second digit using ring electrodes (median nerve). The sensory threshold is first determined by gradually increasing electrical current stimulations of 0.5 ms duration, and the participant indicated the lowest current intensity that is felt. Standard recording electrodes are placed with the recording electrode over the contracting abductor pollicis brevis (APB) muscle, and the reference electrode at the base of

nPROOFS1-v1.2 [01-July-2018] Page 46 of 53

the thumb. The patient abducts the thumb at steady sub-maximal contraction. The technician provides downwards resistance, using EMG sound to provide auditory feedback and semi-quantitatively ensure that contraction is approximately 50% of maximal. While the participant is maintaining this contraction, 10 consecutive electrical stimuli of 15 times the sensory threshold are delivered to the index finger. If the CSPs obtained are poorly formed or absent, and the patient does not perceive the stimuli as painful, then stimulus intensity is increased in 10 mA increments up to 100 mA. Traces are then averaged and rectified. The CSP onset latency is then quantitatively defined by the time after stimulation when the EMG signal drops below 50% of baseline, and the CSP duration is defined by the time period when the EMG signal was less than 50% of the baseline (see Figure below).

Top – Control: normal onset latency and duration Bottom – Patient: abnormal prolonged onset latency and shortened duration

The process is repeated in the lower extremities in a similar manner, using a stimulating probe behind the lateral malleolus (sural nerve), with the recording electrode over the belly of tibialis anterior whilst the patient maintains steady ankle dorsiflexion.

[figure not shown]
Reference values for CSP are taken from St Vincent's Hospital Melbourne reference values for small fibre testing, as below

	Onset (ms)	SD (ms)	ULN (ms)	Duration (ms)	SD (ms)	LLN (ms)
Upper extremity	72.9	7.9	86.4	51.1	9.6	33.8
Lower extremity	100.7	9.2	118.7	54.4	10.7	38.3

n=50 (26 M, 24F). Reference limits are in **bold**.

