11.2.3 Quantitative Sudomotor Axonal Reflex Testing (QSART)

QSART is performed using the Q-Sweat unit (WR Medical Electronics Co., Stillwater, Minnesota), which uses a desiccant pack as its dry air source. Four multi-compartment sweat capsules are placed over standard recording sites on the right side at the forearm, proximal leg, distal leg and foot. A 10% acetylcholine gel is iontophoresed into the skin at a constant current of 2 mA for five minutes to stimulate postganglionic sudomotor unmyelinated nerves, and the sweat responses are assessed during this time plus an additional five minutes (see Figure below).

Example of abnormal reduced sweat volume from foot site.

Reference values for QSART are taken from St Vincent's Hospital Melbourne reference values for small fibre testing, as below

	Total vol (uL)	LLN (uL)	ULN (uL)	Latency	LLN (s)	ULN (s)
Forearm						
Men	2.0	0.5	3.7	102	28	191
Women	1.1	0.3	2.9	82	35	148
Prox Leg						
Men	1.6	0.4	3.9	107	47	197
Women	1.4	0.4	3.9	84	37	153
Distal Leg						
Men	1.9	0.3	3.3	95	24	190
Women	1.2	0.4	3.2	79	38	143
Foot						
Men	1.1	0.2	2.6	128	45	190
Women	0.8	0.2	1.5	116	42	353

n=40 (20 M, 20F). Reference limits are in **bold**.

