To evaluate the effects of a six-month supplementation period with oral long-chain omega-3 PUFA supplements on peripheral nerve health in individuals with type-1 diabetes, as measured by the change from baseline in central corneal nerve fibre length (CNFL) at day 180.

Aim 2

To evaluate the effects of a six-month supplementation period with oral long-chain omega-3 PUFA supplements in individuals with type-1 diabetes on the change from baseline at day 180 for:

Key secondary outcomes:

Other corneal nerve structure and function parameters

[2 main variables for corneal nerve structure: central corneal nerve branch density (CNBD) and central corneal nerve fibre density (CNFD)

2 main variables for corneal nerve function: central corneal sensitivity thresholds to room and cooled temperatures]

Secondary outcomes:

- Patient-reported quality of life

[2 main variables: EQ-5D-5L VAS and Index]

- Small nerve fibre function

[6 main variables: CSP onset latency and duration in the upper limb, CSP onset latency and duration in the lower limb, QSART sweat volume and latency in the foot]

- Large nerve fibre function

[2 symptom/clinical sign composite score variables: MNSI and MDNS (clinical examination) scores]

[3 main neurophysiology variables: sural SNAP amplitude, peroneal motor conduction velocity and tibial minimum F-wave]

- Median nerve excitability

[8 main variables: Depolarising threshold electrotonus (TEd) (peak), TEd (90-100 ms), hyperpolarising threshold electrotonus (Teh) (90-100 ms), TEd (10-20 ms), superexcitability, subexcitability, resting current–voltage (I/V) slope, strength duration time constant]

Aim 3

To evaluate the safety of a six-month supplementation period with oral long-chain omega-3 PUFAs in individuals with type-1 diabetes, by evaluating the incidence of adverse events, change in habitual distance visual acuity, change in intraocular pressure, change in diabetic retinopathy grading, and change in blood pathology parameters from baseline at day 180.

3. Analysis sets/Populations

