R	Insulin intake method	0 = pump 1 = multiple daily injections	< hx_insulin_type>		
R	Concomitant medications	0 = no 1 = yes	<hx_concomitant_medi cations=""></hx_concomitant_medi>		
R	Regular soft contact lens wear (at least once per week)	0 = No 1 = Yes	<ohx_scl></ohx_scl>		
R	History of ophthalmic surgery	0 = No 1 = Yes	<ohx_surgeries></ohx_surgeries>		
D	Diagnosed as having an abnormal small fibre function using either QSART or CSP	0 = Normal 1 = Abnormal	<sfn_qsart_csp></sfn_qsart_csp>		
R	Completed study	0 = No 1 = Yes	<completed_study></completed_study>		
	Primary efficacy				
R	Central Corneal nerve fibre length [right eye]	mm/mm ²	<ivcm_cnfl_c></ivcm_cnfl_c>		
	Secondary and exploratory efficacy outcomes				
	Corneal nerve parameters: main second	ondary			
R	Central corneal nerve fibre density [right eye]	nerves/mm ²	<ivcm_cnfd_c></ivcm_cnfd_c>		
R	Central corneal nerve branch density [right eye]	branches/mm ²	<ivcm_cnbd_c></ivcm_cnbd_c>		
R	Central corneal sensitivity threshold to room temperature [right eye]	mBar	<ncca_rm_c></ncca_rm_c>		
R	Central corneal sensitivity threshold to cooled temperature [right eye]	mBar	<ncca_cd_c></ncca_cd_c>		
	Corneal nerve parameters: explorato	ry			
R	Central corneal dendritic cell density [right eye]	cells/mm2	<ivcm_dcc_c_total></ivcm_dcc_c_total>		
R	Peripheral corneal nerve fibre length [right eye]	mm/mm2	<ivcm_cnfl_p></ivcm_cnfl_p>		

	Variable label	Unit	Variable in data set
R	Peripheral corneal dendritic cell density [right eye]	cells/mm ²	<ivcm_dcc_p_total></ivcm_dcc_p_total>
R	Peripheral corneal sensitivity threshold to room temperature [right eye]	mBar	<ncca_rm_p></ncca_rm_p>
R	Peripheral corneal sensitivity threshold to cooled temperature [right eye]	mBar	<ncca_cd_p></ncca_cd_p>
	Quality of life: secondary		
D	Change in health state: EQ-5D-5L index score	Range: -0.569 to 1	<eq5d5l_index></eq5d5l_index>
R	Change in health state: EQ-5D-5L VAS score	Range: 0 to 100	<eq5d5l_vas></eq5d5l_vas>
	Small fibre function: secondary		
R	Cutaneous silent period - upper limb latency	ms	<csp_upper_lat></csp_upper_lat>
R	Cutaneous silent period - upper limb duration	ms	<csp_upper_duration></csp_upper_duration>
R	Cutaneous silent period - lower limb latency	ms	<csp_lower_lat></csp_lower_lat>
R	Cutaneous silent period - lower limb duration	ms	<csp_lower_duration></csp_lower_duration>
R	QSART sweat volume - measured at the foot	μL	<qsart_foot_vol></qsart_foot_vol>

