R	Nerve excitability: Superexcitability at 5 ms (%)	%	<nes_31_refractoriness _5></nes_31_refractoriness
R	Nerve excitability: TEd20(peak)	-	<nes_32_ted20_peak></nes_32_ted20_peak>
	Signs of dry eye disease: exploratory	•	
D	Ocular Surface Disease Index score	score 0 - 100	<ocul_osdi></ocul_osdi>
R	Tear osmolarity (highest of the two eyes)	mOsmol/L	<ocul_osmol_highest></ocul_osmol_highest>
R	Sodium fluorescein tear break-up time in the right eye (average of three repeat measurements)	S	<ocul_nafl_tbut_r></ocul_nafl_tbut_r>
R	Phenol red thread test (average of	mm	<ocul_prt_ave></ocul_prt_ave>

	Variable label	Unit	Variable in data set
	both eyes)		
R	Anterior blepharitis grading (average of both eyes)	Efron scale score 0-4 (continuous)	<ocul_bleph_ave></ocul_bleph_ave>
R	Meibomian gland dysfunction grading (average of both eyes)	Efron scale score 0-4 (continuous)	<ocul_mgd_ave></ocul_mgd_ave>
R	Conjunctival redness grading (average of both eyes)	Efron scale score 0-4 (continuous)	<ocul_conj_red_ave></ocul_conj_red_ave>
R	Limbal redness grading (average of both eyes)	Efron scale score 0-4 (continuous)	<ocul_limbal_red_ave></ocul_limbal_red_ave>
R	Corneal sodium fluorescein staining score (average of both eyes)	Oxford Score 0-4 (continuous)	<ocul_nafl_stain_ave></ocul_nafl_stain_ave>
	Indirect healthcare costs: exploratory		
D	iMTA iPCQ - loss of productivity due to absences from paid work	hours	<imta_absenteeism></imta_absenteeism>
D	iMTA iPCQ - loss of productivity due to presenteeism	hours	<imta_presenteeism></imta_presenteeism>
D	iMTA iPCQ - loss of productivity of unpaid work	hours	<imta_unpaid></imta_unpaid>
	Safety outcomes		
R	Habitual distance visual acuity measured using a standard eye chart - Right eye	LogMAR	<ocul_va_r_logmar></ocul_va_r_logmar>
R	Habitual distance visual acuity measured using a standard eye chart - Left eye	LogMAR	<ocul_va_l_logmar></ocul_va_l_logmar>
R	Intraocular pressure - Right eye	mmHg	<ocul_iop_r></ocul_iop_r>
R	Intraocular pressure - Left eye	mmHg	<ocul_iop_l></ocul_iop_l>
R	Diabetic retinopathy grading - Worst eye retinopathy grading	6 Grades: 0 = None 1 = Minimal 2 = Mild 3 = Moderate 4 = Severe 5 = Proliferative	<dr_retinopathy></dr_retinopathy>
R	Diabetic macular oedema grading - Worst eye macular oedema grading	3 Grades: 0 = None 1 = Macular oedema 2 = Clinically significant macular oedema	<dr_dme></dr_dme>
R	Bloods: HbA1C, mmol/mol	mmol/mol	<bt_hba1c_mmol></bt_hba1c_mmol>

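### Cutaneous silent periods are recorded on both sides but analysed from one unnamed side, which gives up precision on four of the six small-fibre secondary variables and leaves them undefined

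*Combined protocol and SAP*

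**What the plan says.** **Recording.** Protocol 11.2.2: "The CSP is recorded from both upper and both lower extremities using the same EMG device above". Section 11.2 places this testing at Visits 2 and 5.

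**Analysis.** Protocol 8.1: "For neurophysiological data, analyses will be performed on data from one limb only". No side is given. The sentence cannot be meant literally, because arm and leg are separate outcomes. Protocol 5.1.2 lists "Cutaneous silent period testing: upper and lower limb", and SAP section 2 (Aim 2) counts "6 main variables: CSP onset latency and duration in the upper limb, CSP onset latency and duration in the lower limb", the other two being QSART volume and latency at the foot. The workable reading is one side at each level.

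**Variables.** SAP Appendix 1 has entries such as "Cutaneous silent period - upper limb latency", with no side and no averaging label. Appendix 3 repeats the four CSP variables in the same form, and Appendix 2 gives no derivation for them. The SAP neither repeats nor replaces the one-limb rule, and its closing list of changes from the planned analysis does not mention CSP.

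**Contrast.** Elsewhere the side is settled. Nerve conduction (protocol 11.2.1) is done by "examining the right upper and lower extremities". QSART (11.2.3) capsules are placed "on the right side at the forearm, proximal leg, distal leg and foot". For eye data, SAP Appendix 1 states whether a variable is the right eye, the average of two eyes or the higher of the two.

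**The concern.** A one-limb rule suits nerve conduction and QSART, which are done on the right only. CSP is the exception: the second side is measured at both visits and then has no stated role in the analysis. Three things follow.

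- **Precision.** CSP supplies four of the six small-fibre secondary variables in a trial whose recruitment target was cut to 43. Measurements that would narrow the confidence intervals are already required by the protocol.
- **Definition.** Right, left or the better-formed trace would all satisfy the text. Protocol 11.2.2 expects that some responses will be weak or missing, so the question will arise in practice.
- **Subgroup membership.** The baseline small-fibre neuropathy flag (abnormal QSART or CSP) defines an exploratory subgroup for CNFL in SAP section 7. Nothing says whether a single named side or either side decides that CSP is abnormal.

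**Working it through.** **1. The plan's own figure.** The only sample-size calculation is for CNFL (protocol 2.4.1): difference 2.9, SD 3.2, two-sided 5%, 80% power. The two-sample t-test solution is 20.12, so 21 per group; 21/(1 − 0.15) = 24.7, so 25. Both stated figures reproduce. No power is stated for CSP, so there is no CSP figure to reproduce.

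**2. Count.** Recorded per visit: 2 sides × 2 levels × 2 measures (onset, duration) = 8 values. Analysed, at one side per level: 4.

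**3. Precision.** Assume both sides are equally variable and let r be the between-side correlation of the quantity analysed. The variance of the two-side mean relative to one side is (1+r)/2, the standard error factor is sqrt((1+r)/2), and the equivalent gain in participants is 2/(1+r) − 1. The documents give no r, so a range is shown.

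| Assumed r | Variance factor | SE factor | Equivalent extra participants |
|---|---|---|---|
| 0.3 | 0.65 | 0.81 | 54% |
| 0.5 | 0.75 | 0.87 | 33% |
| 0.7 | 0.85 | 0.92 | 18% |
| 0.8 | 0.90 | 0.95 | 11% |

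**4. On the millisecond scale.** Take lower-limb onset with SD 9.2 ms (reference table in protocol 11.2.2). Assume 20 and 19 participants, as in the motor nerve conduction table at Day 180 (Table S5), because the documents contain no CSP results table. One side: (1.960 + 0.842) × 9.2 × sqrt(1/20 + 1/19) = 8.26 ms detectable at 80% power. Both sides: 8.26 × 0.866 = 7.15 ms at r = 0.5, and 8.26 × 0.949 = 7.83 ms at r = 0.8. The SD is a single-occasion value from a reference sample, not the SD of a baseline-adjusted change in this trial. The milliseconds are therefore illustrative; the ratio is the result.

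**5. Why the flag is a separate matter.** The upper limit of normal for lower-limb onset is 118.7 ms. Illustrative onsets of 125 and 105 ms average (125 + 105)/2 = 115 ms. One side is abnormal and the mean is not, so averaging could move a participant between subgroups.

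**The case against.** Using one side of a paired measurement is a legitimate and unbiased way to avoid within-person dependence, and this trial does it elsewhere: tear break-up time is measured in both eyes (protocol 11.1.15) but analysed in the right eye (SAP Appendix 1). That stands. The point is about precision and definition, not validity.

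A reader might infer that half the information is thrown away. The documents do not support that. Half is a count of values; the variance saved by averaging is (1−r)/2, which reaches one half only if the sides are uncorrelated and shrinks to nothing as r approaches 1.

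A reader might also infer that the side could be picked to favour an arm. Protocol 3.7.1 masks investigators, outcome assessors and data analysts, and protocol 8.1 requires the SAP to be final before unmasking. A side chosen while masked cannot favour an arm. The documents do not say when the side was chosen, so this limits the worry without removing it. Right is the natural guess, given nerve conduction and QSART, but it remains a guess.

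Finally, these are secondary outcomes with unadjusted p-values, which SAP section 7.1.1 already says to interpret with caution. That is a fair reason to keep the point in proportion.

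**Conclusion.** The point holds as a modest and inexpensive improvement. CSP is recorded bilaterally, the analysis rule keeps one unnamed side, and the SAP does not fill the gap. Four of the six small-fibre secondary variables are affected. The gain from averaging is a standard error 5% to 19% smaller for r between 0.8 and 0.3. It rests on an assumed r, equal variability on the two sides, and a treatment effect that is the same on both.

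The one-side analysis is not biased, and no misuse of the choice is shown. The CNFL sample size and the primary and key secondary analyses are untouched. The only link to the primary outcome is membership of the exploratory small-fibre neuropathy subgroup.

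**What to change.** 1. In protocol 8.1 and SAP Appendices 1 to 3, define each CSP onset and duration variable as the mean of right and left at each visit. Where only one side is measurable at that visit, use that side.
2. Fix before unmasking how an absent CSP is coded, since neither a latency nor a mean exists for it.
3. Report a right-side-only analysis as a sensitivity check.
4. Do not redefine the small-fibre neuropathy flag as side-averaged. Keep it clinically derived, and state before unmasking whether one named side or either side being abnormal counts, consistent with how the reference limits in protocol 11.2.2 were built; the protocol does not say whether those limits apply per side or to a mean.
5. Keep the right-side rule for nerve conduction and QSART.

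The cost is one derived variable and some wording; no new testing is needed. The small downside is that some visits will rest on one side and be less precise. The file also holds results by arm, so for this trial the pre-unmasking steps can now only be met by documenting what was decided and when. A two-side analysis added at this stage should be labelled post hoc.

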8.1.1. Populations to be analysed

The statistical analysis will follow an intention-to-treat approach (i.e., will include data from all participants randomised into the study, regardless of whether they received the study intervention). This approach preserves the prognostic balance in the study arms achieved by randomisation.

8.1.2. Handling of missing data

The proposed statistical approach provides valid inference in the presence of missing data if the missing data mechanism is ignorable (missing completely at random or missing at random) and includes participants who have a baseline and at least one post-baseline measurement of the primary outcome measure (CNFL). Missing values will be checked and reported across treatment arms and follow-up time points.

8.1.3. Methods of analysis

The primary outcome measure is the change in central corneal nerve fibre length (CNFL) from baseline (Day 1); the primary analysis endpoint is Day 180 (six months).

A range of secondary outcome measures, including safety outcomes, will be investigated (as detailed in Section 5.1).

For continuous outcome measures, a repeated measures model will be used to assess for differences in the post-treatment means between groups (i.e., the main effect of group) at each time point, with the baseline (Day 1) values used as a covariate. For binary and categorical outcome measures, an ordered logistical regression model will be used. For all analyses, an alpha level of 0.05 will be adopted for statistical significance. Unless otherwise specified, data will be expressed as mean plus/minus standard deviation.

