7.1.1 Multiple testing

The primary outcome at day 180 will be evaluated using the two-sided 5% level of significance.

Multiple testing for the key secondary outcomes related to corneal nerve parameters at day 180 will be assessed using the Benjamini-Hochberg stepwise method with a false discovery rate of 5% for: corneal nerve fibre density (CNFD), corneal nerve branch density (CNBD), central corneal sensitivity thresholds to room temperature, and central corneal sensitivity thresholds to cooled temperature. For these key secondary outcomes at day 180, we will report the multiplicity adjusted p-values.

For all other post-baseline time points and outcomes, we will report multiplicity unadjusted p-values. Given the large number of statistical tests, the probability of finding at least one false positive finding will be close to 100%. For this reason, we will exercise caution and in addition to p-values, associations will be interpreted based on the magnitude and direction of the association and width of the 95% confidence intervals.

All tests will be performed two-sided, and we will report two-sided 95% confidence intervals.

8. Sensitivity Analyses

Additional sensitivity analyses will be performed for the outcomes linked to the primary and key secondary aims for the following dataset:

- Dataset excluding participants deemed non-compliant (see definition in Section 6.3).

9. QC Plans

Source data verification of the data entered on REDCap was performed by the Principal Investigator (PI). Data was manually checked for accuracy from the source worksheets/original digital data record, for all participants, for the primary outcome (CNFL) and key secondary outcomes (CNFD, CNBD, central corneal sensitivity thresholds to room temperature, and central corneal sensitivity thresholds to cooled temperature). In addition, a subset of data comprising at least 20% of the full dataset,

was randomly selected by the PI for verification, to ensure that the observations and findings are recorded correctly and completely. Data found as incorrectly entered were verified against the original source documents, corrected on REDCap and recorded accordingly.

10. Programming Plans

A list of all planned tables and figures and their templates can be found in Appendix 4.

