- 3. Between-group comparisons of dry eye symptom scores using the exploratory outcome of Ocular Surface Disease Index (OSDI) (appendix 3) could not be performed using the prespecified repeated measures model due to the number of scores with the value of zero. For the OSDI outcome, comparison of change between the omega-3 PUFA and placebo groups was tested using the non-parametric Wilcoxon rank sum test. The estimate and 95% confidence intervals between-groups were obtained using the Hodges-Lehman non-parametric estimator.
- 4. Total omega-3 concentrations (%) are not additionally analysed as EPA and DHA concentrations have been reported.
- 5. Exploratory outcomes for indirect health care were not analysed.

[figure not shown]

Figure S1. CONSORT diagram. PUFA=polyunsaturated fatty acid. ^aOne participant in the omega-3 PUFA group completed the study but did not undergo procedures relating to small or large nerve fibre function in the limbs.

[figure not shown]

Figure S2. Axonal nerve excitability studies at baseline and endpoint (Intention-To-Treat sample). Threshold electrotonus at day 0 (dashed line) and day 180 (solid line) in (A) the omega-3 PUFA group and (B) the placebo group. *Asterisk indicates significant between-group difference for change in hyperpolarising threshold electrotonus at the 90-100ms interval (TEh 90-100 ms) during a -40% control threshold stimulus.

Table S1. Summary of concomitant systemic medications (Intention-To-Treat sample)

Medication category	Omega-3 PUFAs	Placebo
	(n=21)	(n=22)
None	5 [24%]	7 [32%]
At least one concomitant medication	16 [76%]	15 [68%]
Blood Products and Modifiers	1 [5%]	1 [5%]
Analgesics	2 [10%]	3 [14%]
Antibacterials	1 [5%]	1 [5%]
Anticonvulsants	0 [0%]	2 [9%]
Antidepressants	1 [5%]	3 [14%]
Antiparasitics	0 [0%]	1 [5%]
Blood Glucose Regulators	1 [5%]	0 [0%]
Cardiovascular agents	15 [71%]	13 [59%]
Contraceptives	2 [10%]	1 [5%]
Dermatological agents	1 [5%]	3 [59%]
Electrolytes/Minerals/Metals/ Vitamins	12 [57%]	6 [27%]
Vitamins	7 [33%]	5 [23%]
Electrolyte/Mineral Replacement	5 [24%]	1 [5%]
Gastrointestinal Agents	3 [14%]	0 [0%]
Genetic or Enzyme Disorder: Replacement, Modifiers, Treatment	1 [5%]	1 [5%]
Hormonal Agents, Stimulant/Replacement/ Modifying (Thyroid)	1 [5%]	2 [9%]
Immunological Agents	1 [5%]	1 [5%]
Inflammatory Bowel Disease Agents	0 [0%]	1 [5%]
Respiratory Tract/ Pulmonary Agents	2 [10%]	1 [5%]
Sleep Disorder Agents	1 [5%]	0 [0%]

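### Protocol and SAP leave it unsettled whether an unadjusted p below 0.05 on the 21 other secondary outcomes may be called significant, and the Figure S2 legend calls one such result (p=0.044) significant without caveat

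*Combined protocol and SAP*

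**What the plan says.** - **Protocol 8.1.3 (Methods of analysis)** gives one rule for everything: "For all analyses, an alpha level of 0.05 will be adopted for statistical significance".
- **SAP 7.1.1 (Multiple testing)** is narrower. For CNFL: "The primary outcome at day 180 will be evaluated using the two-sided 5% level of significance". For the next tier: "Multiple testing for the key secondary outcomes related to corneal nerve parameters at day 180 will be assessed using the Benjamini-Hochberg stepwise method", at a false discovery rate of 5%. That tier has four outcomes: nerve fibre density, nerve branch density, and the two central corneal sensitivity thresholds.
- For the rest, the same section says: "For all other post-baseline time points and outcomes, we will report multiplicity unadjusted p-values". It adds that "the probability of finding at least one false positive finding will be close to 100" per cent, and undertakes to interpret cautiously from the size and direction of effects and the width of the intervals. It sets no significance threshold for these outcomes.
- **SAP section 2, Aim 2** lists the remaining secondary outcomes: 2 quality of life, 6 small fibre, 2 large-fibre composite scores, 3 large-fibre neurophysiology and 8 median nerve excitability variables.
- **Figure S2 legend**, in the supplementary results that follow the SAP: "Asterisk indicates significant between-group difference for change in hyperpolarising threshold electrotonus at the 90-100ms interval". Table S8 gives that result as -9.33 (95% CI -18.41 to -0.25), p=0.044, and its footnote says the p-values are unadjusted. The legend has no such note.

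**The concern.** The two rules give different answers to a simple question: does an unadjusted p below 0.05 on one of the 21 outcomes count as a significant result? The protocol sentence says yes. The SAP warns that false positives are almost certain, but never withdraws the protocol sentence for these outcomes.

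The gap matters because 19 of the 21 (all except the two EQ-5D-5L scores) are neuropathy scores or measures of limb nerve function. They are the main planned evidence on whether any effect extends beyond the cornea. The legend presents one of them as significant without a caveat, so a plausible chance finding can be read as an established effect on limb nerves.

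**Working it through.** **1. Number of outcomes.** SAP Aim 2: 2 + 6 + 2 + 3 + 8 = 21.

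**2. The SAP's own figure.** For k independent tests at 0.05 with no true effects, P(at least one p<0.05) = 1 - 0.95^k. A hand count of SAP Appendix 1 gives about 129 unadjusted Day 180 variables, so 1 - 0.95^129 = 0.9987. The value already reaches 0.95 at k = 59 and 0.99 at k = 90. The SAP's statement is reproduced.

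**3. The same quantity for the outcomes at issue.** SAP 7.1.1 makes the tests two-sided ("All tests will be performed two-sided, and we will report two-sided 95% confidence intervals"). Under independence: 1 - 0.95^21 = 0.659, with 21 × 0.05 = 1.05 false positives expected; and 1 - 0.95^8 = 0.337. The documents give no correlations between outcomes, so an equal correlation r was assumed and 200,000 sets of two-sided z-tests were simulated:

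| Outcomes | r = 0 | r = 0.3 | r = 0.5 | r = 0.8 |
|---|---|---|---|---|
| 21 secondaries | 66% | 56% | 43% | 23% |
| 8 excitability | 34% | 30% | 25% | 16% |

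**4. The marked p-value.** From the interval in Table S8, SE = (18.41 - 0.25)/(2 × 1.96) = 4.63; z = 9.33/4.63 = 2.01; two-sided p = 0.044. This agrees with the table.

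**5. Adjustment over the eight excitability variables.** Sorted p-values from Table S8: 0.044, 0.31, 0.32, 0.40, 0.42, 0.73, 0.74, 0.88.
- Holm, smallest p: 8 × 0.044 = 0.352.
- Benjamini-Hochberg, smallest p: the minimum over ranks j of 8 × p(j)/j. Rank 1 gives 0.352. The lowest later term is 8 × 0.42/5 = 0.672. The adjusted value is 0.352.

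**6. Adjustment over all 21.** Ten p-values are in the documents: the eight above, peroneal motor velocity (0.99, Table S5) and sural amplitude (0.85, Table S6). Eleven are not.
- Nine of the ten known values exceed 0.044, so TEh 90-100 ms can rank no lower than 12th. The smallest possible Benjamini-Hochberg value is 21 × 0.044/12 = 0.077.
- If all eleven missing values were 1, it would be 21 × 0.044 = 0.924, which is also the Bonferroni value.
- It therefore lies between 0.077 and 0.924 and cannot reach 0.05.

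**The case against.** The strongest reply is that the SAP has already dealt with this. The protocol defers to a separate plan. That plan ties error rates to CNFL and four named outcomes, declares that everything else is unadjusted, states the consequence candidly and promises caution. The SAP's Table 3 template, which covers all 21, carries a footnote that p-values are unadjusted. Table S8 has the same footnote and is titled as exploratory. This stands: the lack of adjustment is a declared choice, not a hidden fault, and requiring Benjamini-Hochberg within each domain would be a preference.

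Other limits also stand:
- The SAP lists the eight excitability variables under one heading but does not make them a multiplicity family. The 0.35 rests on a grouping chosen for this review.
- A reader might infer that the legend shows the protocol's 0.05 rule in operation. The documents do not establish that. TEh 10-20 ms and TEh 20-40 ms each have p=0.019 in Table S8, yet the legend does not mention them.
- A reader might set the 43% against the stated 5% and call it a ninefold inflation. That compares a familywise rate with a per-test level. The SAP states no 5% familywise rate for these outcomes; the only familywise figure it gives is the near-certainty reproduced above.

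The two neighbouring electrotonus intervals might be offered as support for the marked result. They are unadjusted too. Table S8 prints 29 rows, one without a p-value in the text available. Whatever that value is, Benjamini-Hochberg over the 29 gives at least 29 × 0.019/3 = 0.18 for those two and at least 29 × 0.044/4 = 0.32 for TEh 90-100 ms.

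None of this answers the narrow point. No text says when the word significant may be used for the 21, and the legend uses it without the caveat that the SAP's caution calls for.

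**Conclusion.** The point holds as an inconsistency of rule and wording, with one visible consequence. Protocol 8.1.3 and SAP 7.1.1 need reconciling, and the Figure S2 label is at odds with the SAP's caution. The label does not survive adjustment over the eight excitability variables (0.35) or over all 21 (0.077 at the very least). The chance figures, 23% to 66% for the 21 and 16% to 34% for the eight, assume no true effects and a common correlation between 0.8 and 0. They describe the risk and contradict no stated error rate.

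A reader might infer that the trial's main conclusion depends on these outcomes. It does not: SAP Aim 1 measures peripheral nerve health by central CNFL. Neither the CNFL result nor the four key secondary results are touched. What changes is what may be concluded about limb nerves from the one marked variable.

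**What to change.** Results are already known, so issue a dated clarification and leave the original text on record. It should say that:
- claims of statistical significance are confined to CNFL at Day 180 (two-sided 5%) and the four key secondary outcomes (Benjamini-Hochberg, false discovery rate 5%);
- the general 0.05 sentence in protocol 8.1.3 is to be read in that sense;
- the other 21 secondary outcomes are reported as estimates with 95% confidence intervals and unadjusted p-values, with no significance symbols.

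In the Figure S2 legend, replace the word significant with *unadjusted p=0.044 (Benjamini-Hochberg 0.35 over the eight excitability outcomes)*, or remove the asterisk.

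The cost is a short note and one legend, with no new data or model fitting. The downside is the loss of one nominally significant secondary result.
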